7.3 Analysis Plan

- **7.3.1** Study Populations There will be three study populations the modified Intent-to-treat (mITT), Per Proocol (PP), and Immunogenicity populations. The mITT Population includes any participant that was enrolled, randomized into the study, and received vaccine. The PP Population is a subset of the ITT Population excluding those participants with major protocol violations. The Immunogenicity Population is a subset of the mITT Population that includes only subjects who received vaccine, provide baseline and Visit 4 blood draws available for analysis within the protocol-defined time frame, and with no protocol violations affecting immunogenicity. These protocol violations will be listed in the Statistical Analysis Plan. Statistical analyses of the safety outcomes will be performed for both mITT and PP populations, and immunogenic outcomes will be analyzed for the Immunogenicity Population.
- **7.3.2** Alpha Level No adjustment to the alpha level will be made for the secondary and exploratory objectives.
- **7.3.3** Primary Objective To compare the proportions of adverse birth outcomes in pregnant women vaccinated with RIV4 versus IIV4.
 - Research hypothesis: The proportion of pregnant women with adverse birth outcomes will be non-inferior (not higher based on the noninferiority margin) after receipt of RIV4 compared to IIV4.

This objective will be assessed using a one-sided noninferiority test with the alpha level set at 0.025 (1-sided) and a noninferiority margin of 10%.

The null hypothesis assumes that RIV4 is inferior to IIV4 in regards to the proportion of pregnant women with adverse birth outcomes.

Ho: RIV4 - IIV4
$$\geq$$
 0.10 (10%)

The alternative hypothesis states that RIV4 is noninferior to IIV4 in regards to the proportion of pregnant women with adverse birth outcomes.

The upper bound of a stratified (by study site) Newcombe binomial confidence interval (Yan and Su 2010) with Cochran-Mantel-Haenszel (CMH) weighting of the difference will be used to make this assessment.

A composite outcome for adverse birth outcome [defined by the occurrence of at least one of the following events: preterm birth, spontaneous abortion, fetal death or neonatal death] will be used as the primary study endpoint.

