#### **3.3 Exploratory**

- a)
  - 1. EOM1.1: Frequency and descriptions of serious adverse events in pregnant women vaccinated with RIV4 versus IIV4 during the 42 days after vaccination.
  - 2. EOM1.2: Frequency and descriptions of serious adverse events in pregnant women vaccinated with RIV4 versus IIV4 during the study
- b)
  - 1. EOM2.1. Proportions of infants born small-for-gestational age after RIV4 versus IIV4 vaccination.
  - 2. EOM2.2: Proportion of pregnant women with clinical chorioamnionitis after RIV4 versus IIV4 vaccination.
  - 3. EOM2.3: Proportion of women with preeclampsia or eclampsia after RIV4 versus IIV4 vaccination.

c)

1. EOM3.1: Proportion of infants with medically-attended events through 90 days of life after maternal RIV4 versus IIV4 vaccination.
2. EOM3.2: Frequency and description of SAEs in infants through 90 days of life after maternal RIV4 versus IIV4 vaccination.
3. EOM3.3 Proportion of infants with neonatal death after maternal RIV4 versus IIV4 vaccination.

d)

1. EOM4.1: Proportion of pregnant women achieving seroconversion at day 29 after RIV4 versus IIV4 vaccination [a Hemagglutination Inhibition Assay (HAI) titer  $\geq 1:40$  at day 29 if the baseline titer is  $< 1:10$  or a minimum four-fold rise in HAI titer if the baseline titer is  $\geq 1:10$ ) for each influenza vaccine antigen].
2. EOM4.2: Proportion of pregnant women with a seroprotective HAI titer ( $\geq 1:40$ ) post-vaccination at day 29 after RIV4 versus IIV4 vaccination for each influenza vaccine antigen.
3. EOM4.3: The maternal geometric mean HAI titer (GMT) pre and post-vaccination at day 29 after RIV4 versus IIV4 for each influenza vaccine antigen and the post/pre-vaccination ratio.

e)

1. EOM5.1: Proportion of infants with cord blood seroprotective HAI titer ( $\geq 1:40$ ) for each influenza vaccine antigen after maternal RIV4 versus IIV4 vaccination.
2. EOM5.2: Infant cord blood geometric mean HAI titer (GMT) for each influenza vaccine antigen after maternal RIV4 versus IIV4 vaccination.
3. EOM5.3: Ratio of cord blood to maternal influenza antibody titers at time of delivery for each influenza vaccine antigen after maternal RIV4 versus IIV4 vaccination.

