#### **6.3 Maternal Immunogenicity Population**

The Maternal Immunogenicity Population is a subset of the mITT Population that includes only pregnant women participants who received study vaccine, provide baseline and post-vaccination Visit 4 blood draws available for analysis within the protocol-defined time frame,

and with no major protocol violations affecting immunogenicity as determined by the study investigators.

The mITT Population is the primary analysis population for the safety and health outcomes analyses, with the PP Population as a confirmatory analysis population. The Immunogenicity Population is the primary analysis population for maternal immunogenicity outcomes (Exploratory Objectives 5); otherwise the mITT Population will be used for the Exploratory Objectives.

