The ratio and 95% confidence interval for cord blood to maternal influenza antibody titers at time of delivery for each influenza vaccine antigen after maternal RIV4 versus IIV4 vaccination will be presented. Non-overlapping confidence boundaries will be an indication of a statistical difference between the groups. The proportion and 95% exact binomial confidence interval will also be presented in tabular format for each group. The Immunogenicity Population is the primary analysis population.

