## **APPENDIX 1**

### **Major Protocol Violations for Analysis**

1. Major Protocol Violations for Exclusion from Per Protocol Populations:
  - a. Age < 18 years of age at enrollment
  - b. Gestational age >34 weeks at vaccination
  - c. Did not provide written informed consent prior to vaccination
  - d. End of participation in study (e.g. loss to follow-up, early termination/withdrawal) prior to end of pregnancy
  - e. Receipt of the year's influenza vaccine (2019-20 or 2020-21) prior to study enrollment
  - f. Study participation in both 2019-20 and 2020-21 influenza season
  - g. Receipt of live vaccine while participating in this study or receipt of non-study vaccine within 7 days before or during the 8 days post-vaccination period.
  - h. Receipt of experimental drugs or medical device while participating in this study
  - i. Known multi-fetal gestation or fetal congenital anomaly at the time of enrollment, e.g. genetic abnormality or major congenital malformation based on antenatal ultrasound before randomization
2. Major Protocol Violations for Exclusion from Immunogenicity Populations:
  - a. No vaccine received
  - b. No pre- and/or post-vaccination blood draw
  - c. Receipt of any other vaccine between the pre- and post-vaccination blood draws
  - d. New immunosuppression disorders between the pre- and post-vaccination blood draws or receipt of immunosuppressive medication between the pre- and post-vaccination blood draws
  - e. Subject who was inadvertently enrolled and randomized to the study, though they were later learned to have had met the following criteria for study exclusion that would have affected immunogenicity
  - f. Influenza vaccine receipt during the current influenza season prior to study enrollment
  - g. Use of oral, antenatal, or parenteral corticosteroids ( $\geq$  20mg/day prednisone equivalent) or high-dose inhaled glucocorticoid for  $\geq$  14 consecutive days within the preceding 30 days
  - h. Has an active neoplastic disease (excluding non-melanoma skin cancer), a history of any hematologic malignancy, current bleeding disorder, or taking anticoagulants (a daily aspirin is acceptable)
  - i. Has a history of receiving immunoglobulin or other blood product (with exception of Rh immunoglobulin) within the 3 months prior to study vaccination

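### The SAP names conflicting populations for the cord-blood objective (EO6), and one of them requires a Visit 4 maternal draw that no cord-blood endpoint uses

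*SAP*

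**What the plan says.** The cord-blood objective is EO5 in SAP 2.3 but EO6 in SAP 8.3, where a reactogenicity objective has been inserted ahead of it. Its endpoints keep the numbers EOM5.1 to EOM5.3. I use EO6 below.

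- **SAP 8.3, EO6:** "The Immunogenicity Population is the primary analysis population". The SAP does not define that exact term. Section 6.3 defines a Maternal Immunogenicity Population, whose members must "provide baseline and post-vaccination Visit 4 blood draws available for analysis within the protocol-defined time frame". Appendix 1, list 2, item b excludes a woman with "No pre- and/or post-vaccination blood draw".
- **Protocol 7.3.1:** "immunogenic outcomes will be analyzed for the Immunogenicity Population", with the same two draws required.
- **SAP 6.3:** the immunogenicity population is primary for maternal immunogenicity outcomes; "otherwise the mITT Population will be used for the Exploratory Objectives".
- **SAP 9:** if more than 10% of the Maternal Immunogenicity Population have major violations affecting immunogenicity, an EO6 sensitivity analysis drops those mothers' cord data, and its results are set against the mITT results.
- **SAP 3.3, endpoints:** "Proportion of infants with cord blood seroprotective HAI titer"; "Infant cord blood geometric mean HAI titer (GMT) for each influenza vaccine antigen"; and "Ratio of cord blood to maternal influenza antibody titers at time of delivery for each influenza vaccine antigen".

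**The concern.** Requiring both a baseline and a Visit 4 draw makes sense for seroconversion and the post/pre ratio, which use both titres. The cord endpoints use neither. If the EO6 sentence governs, a woman with a good cord sample drops out of the cord analysis because she missed Visit 4 or came outside its window.

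Two things make this worth settling. Cord samples are already limited: they are planned at Duke and collected at the other two sites only if feasible. The loss is also not purely random. Some of it falls on women who deliver before the Visit 4 window opens and do not come back for the draw. These are the shortest intervals from vaccination to delivery, and preterm birth is a component of the primary endpoint.

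If instead SAP 6.3 governs, none of this happens. At present two analysts could follow different sections and report different cord-blood results.

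**Working it through.** The plan states no sample size, precision or expected loss for the cord-blood objective, so there is no figure of its own to reproduce.

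**Step 1. Titres used against draws required.**

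| Endpoint (SAP 3.3) | Titres used | Draws required if the EO6 sentence governs |
|---|---|---|
| EOM5.1, seroprotection in cord blood | cord | baseline and in-window Visit 4 |
| EOM5.2, cord GMT | cord | baseline and in-window Visit 4 |
| EOM5.3, cord to maternal ratio | cord and maternal at delivery | baseline and in-window Visit 4 |

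**Step 2. Which population governs.**

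| Place | Population for cord outcomes | Visit 4 draw needed |
|---|---|---|
| SAP 8.3, EO6 | Immunogenicity | yes |
| Protocol 7.3.1 | Immunogenicity | yes |
| SAP 6.3 | mITT | no |
| SAP 9 | set without violators, compared with mITT | not for the mITT result |

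The section 9 safeguard does not resolve this. Its 10% trigger is counted within the Maternal Immunogenicity Population, which by definition has no members with such violations. Read literally, the share is always 0% and the analysis is never triggered.

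**Step 3. Timing.** The latest vaccination is at 34 weeks 0 days, which is 34 × 7 = 238 days. With vaccination as Day 1, Day d falls at 238 + d − 1 days. The protocol's visit description opens the Visit 4 window at Day 21; the −7/+14 window opens it at Day 22.

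- Day 21: 238 + 20 = 258 days = 36 weeks 6 days.
- Day 22: 238 + 21 = 259 days = 37 weeks 0 days.

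Earlier vaccination opens the window at an earlier gestational age. So any live birth before the window opens is before 37 weeks 0 days, and is preterm by the plan's definition. (Counting elapsed days after vaccination instead of study days shifts the second line by one day. The only exception is then a birth at exactly 37 weeks 0 days after vaccination at exactly 34 weeks 0 days.)

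**Step 4. Precision.** If a share f of usable cord samples is lost, equally in both arms, interval width grows by 1/√(1 − f). The documents do not give f; these values are assumed.

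| f | 1/√(1 − f) | Wider by |
|---|---|---|
| 5% | 1/√0.95 = 1.026 | about 3% |
| 10% | 1/√0.90 = 1.054 | about 5% |
| 20% | 1/√0.80 = 1.118 | about 12% |

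**Step 5. How many women deliver before the window opens.** I simulated this under the following assumptions:

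- gestational age at vaccination uniform over 10 to 34 weeks;
- 15% preterm (the plan's composite event rate, taken here as the preterm rate);
- preterm births short of 37 weeks by an exponential amount with mean 2 weeks;
- term births centred at 39 weeks with SD 1 week;
- delivery after vaccination, because a woman who has already delivered cannot be enrolled.

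The shares delivering before Day 22 are:

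- about 1.0% of all women;
- about 3.7% of women vaccinated at 28 weeks or later;
- about 26% of the preterm births in that later group.

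Opening at Day 21 gives slightly less. Each share is an upper limit on the loss from delivery before the window opens, because it assumes that none of these women returns for the draw.

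**The case against.** The strongest objection is that EO6 may not use this population at all. SAP 6.3 confines it to the maternal outcomes and puts the rest in mITT. Section 9 fits that reading: an EO6 sensitivity analysis that removes violators makes little sense if the main analysis has already removed them. This stands. A reader might infer from the EO6 sentence alone that cord samples will be discarded, but the documents do not support that as settled. The firm result is a contradiction, and the loss is conditional on how it is resolved.

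A reader might also infer that every woman who delivers soon after vaccination is excluded. The documents do not say that delivery cancels Visit 4, and a postpartum draw within the window would count. Nor is Day 29 the right cut for counting such women, since a draw is valid from Day 21 or 22.

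A third tempting reading is that the rule biases the comparison between vaccines. The share removed for early delivery would differ by arm only if the vaccines differed on preterm birth. The documents give no evidence of that, and the plan assumes the same 15% event rate in both arms.

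Finally, the objective is exploratory, with no power claim, and collecting samples only if feasible already selects among cord samples. That limits the importance of the point, but it is no reason to keep a requirement that the endpoints do not need.

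**Conclusion.** The point holds as an unresolved conflict with a conditional consequence. SAP 8.3 and protocol 7.3.1 point to one population for the cord-blood outcomes; SAP 6.3 and section 9 point to mITT. If the first prevails, usable cord samples are lost for want of a draw that no cord endpoint uses, and the part of the loss due to early delivery falls on preterm infants.

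The total cannot be computed from the documents. At an assumed loss of 5% to 20%, intervals are about 3% to 12% wider. Delivery before the window opens accounts for at most about 1% of women under the Step 5 assumptions, but up to about a quarter of preterm births after vaccination at 28 weeks or later. The effect is small overall and confined to an exploratory objective. It is worth correcting because the correction is only wording.

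**What to change.** 1. In SAP 8.3 EO6, name and define one cord-blood population: mITT mothers whose infant has a cord HAI result, plus a maternal delivery result for EOM5.3. Require neither the baseline nor the Visit 4 draw (Appendix 1, list 2, item b does not apply). Keep the other list 2 exclusions.
2. Items c and d of list 2 are defined between the two blood draws, an interval that does not exist for a woman without a Visit 4 draw. For EO6, define them from vaccination to delivery. This is a longer interval. Visit 6 records maternal Tdap receipt, so item c would then remove every mother given Tdap, or any other vaccine, after the study vaccine. Count these mothers without reference to arm before fixing the rule. If there are many, end the interval for item c at the close of the Visit 4 window, or at delivery if earlier.
3. Align SAP 6.3, SAP 9 and protocol 7.3.1 with this population, and use one objective number for cord blood throughout the SAP.
4. Base the section 9 10% trigger on mITT mothers with cord samples, so that it can be met.
5. Reconcile the two statements of the Visit 4 window (Days 21 to 42, and 29 −7/+14, that is Days 22 to 43).

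The cost is SAP and protocol wording and one more line in the flow chart; no sample or visit is added. The downside is that the cord-blood set is no longer a subset of the maternal immunogenicity set, which the report should state.

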## **9 SENSITIVITY ANALYSES**

If there are any participants who receive the incorrect treatment (i.e., treatment other than what they were randomized to receive), then in the sensitivity analysis of the primary and secondary objectives, the participants will be analyzed based on the treatment the participant received not what the participant was randomized to receive. For example, if a participant was

randomized to RIV4 but inadvertently received IIV4, that participant would be reassigned to the IIV4 treatment group in the sensitivity analyses.

If more than 10% of the Maternal Immunogenicity Population have major protocol violations affecting immunogenicity as determined by the study investigators, then a sensitivity analysis will be performed for Exploratory Objective 6. No infant cord blood data will be analyzed from mothers with the major protocol violations affecting immunogenicity. These results will be compared with those using the mITT Population to make the best assessment of Exploratory Objective 6.

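### The 10% trigger for the cord-blood sensitivity analysis can never be met, and the plan names two different primary populations for cord blood

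*SAP*

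**What the plan says.** **The trigger.** SAP section 9 sets the condition for a sensitivity analysis of cord blood (Exploratory Objective 6 in section 8.3): "If more than 10% of the Maternal Immunogenicity Population have major protocol violations affecting immunogenicity as determined by the study investigators". If it is met, cord-blood data from mothers with such violations are left out, and "These results will be compared with those using the mITT Population".

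**The population the trigger counts.** SAP section 6.3 builds the Maternal Immunogenicity Population from vaccinated women in the mITT set. Its last condition shuts out violators: "and with no major protocol violations affecting immunogenicity as determined by the study investigators". Another condition concerns sampling, since members must "provide baseline and post-vaccination Visit 4 blood draws available for analysis within the protocol-defined time frame". Appendix 1, item 2, lists the violations under the title "Major Protocol Violations for Exclusion from Immunogenicity Populations".

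**The primary population for cord blood.** Section 6.3 reserves the Immunogenicity Population "for maternal immunogenicity outcomes (Exploratory Objectives 5); otherwise the mITT Population will be used for the Exploratory Objectives". The cord-blood text in section 8.3 ends with a different rule: "The Immunogenicity Population is the primary analysis population". Protocol 7.3.1 says that "immunogenic outcomes will be analyzed for the Immunogenicity Population", without separating maternal from cord-blood outcomes.

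**The concern.** The trigger asks what share of a population has a feature that bars entry to that population. A prespecified analysis that looks like a safeguard is therefore switched off from the start.

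Separately, two analysts following the SAP could report primary cord-blood results in different sets of women, and each could cite a sentence in support. Comparing violation-excluded with mITT results would show whether the choice matters, but that is the comparison the unreachable trigger controls. If the ambiguity is left until titres are available, the choice could be guided by the results.

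**Working it through.** **1. Can the trigger be met?** Let P be the Maternal Immunogenicity Population, of size n, and V the women with major violations affecting immunogenicity.

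- Section 6.3 admits no member of V to P. It uses the same phrase as section 9, including who decides, so no reading of *violation* separates the two.
- Share = |P ∩ V| / |P| = 0/n = 0% for every n. The rule needs more than 10%.
- Protocol 7.3.1 and Appendix 1, item 2, also exclude violators.

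The 10% is a decision threshold, so there is no sample-size figure to reproduce. For scale only, suppose the denominator were the mITT population (an assumption; the SAP does not say so):

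- With all 430 planned women: 0.10 × 430 = 43, so at least 44 violators are needed (44/430 = 10.2%).
- With the roughly 408 expected to be evaluable: 0.10 × 408 = 40.8, so at least 41 are needed (41/408 = 10.05%).

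Another denominator, such as mothers with a cord sample, would give another count. Appendix 1, item 2b, lists a missing pre- or post-vaccination draw as a violation, so whether 2b counts could decide the outcome.

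**2. Which population is primary for cord blood?**

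- SAP 6.3: Immunogenicity Population for maternal outcomes, mITT for the rest. Cord blood is therefore mITT.
- SAP 9: sets the violation-excluded result against mITT, which fits 6.3.
- SAP 8.3, end of the cord-blood text: Immunogenicity Population.
- Protocol 7.3.1: Immunogenicity Population for immunogenic outcomes, which fits 8.3.

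Numbering does not remove the conflict. SAP 2.3 calls cord blood EO5 and has no EO6. SAP 8.3 calls maternal responses EO5 and cord blood EO6. Section 6.3 attaches its number 5 to maternal outcomes, so it follows 8.3. Nor is there a separate cord-blood population: SAP section 6 defines three populations, and section 7.2 refers to three.

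**3. Who moves between the two sets?** The cord-blood measures (EOM5.1 to 5.3 in SAP 3.3) use cord and maternal delivery samples. None uses the Visit 4 sample, yet section 6.3 requires an in-window Visit 4 draw. A mother with a cord sample but no such draw is in under 6.3 and out under 8.3, even with no other violation.

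The protocol's own timing makes this plausible. Vaccination is allowed up to 34 weeks 0 days. A woman vaccinated then, on Day 1, reaches 36 weeks 6 days 20 days later, on Day 21. If she delivers preterm, she delivers by Day 21, before Visit 4 opens on Day 22 in the visit table. The documents do not say that Visit 4 is cancelled after delivery, so this shows a route and not a count.

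The number who move cannot be computed: no expected count of cord samples, missed Visit 4 draws or violations is given. SAP 4.2 plans delivery samples at one of three sites and takes them at the other two only if feasible. The footnote to the protocol's visit table calls them optional without excepting any site.

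**4. Minor, separate: the Visit 4 window that decides membership.**

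- Protocol 5.1, visit description: Days 21 to 42.
- Protocol 5.1, visit table: 29 − 7 to 29 + 14 = Days 22 to 43.
- Protocol 3.2.1 and SAP 4.2 give the same offsets, counted from vaccination. Read as study days: Days 22 to 43. Read as days elapsed since Day 1 (an assumption): 1 + 22 to 1 + 43 = Days 23 to 44.

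On the study-day reading, 2 draw days change status (21 and 43). On the elapsed-day reading, 4 do (21, 22, 43 and 44).

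**The case against.** The literal unreachability of the trigger and the clash between 6.3 and 8.3 are hard to dispute. The case on the other side concerns weight.

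- **The SAP leans towards mITT.** Section 6.3 limits the Immunogenicity Population in words to maternal outcomes, and the comparison in section 9 makes most sense if mITT is primary. The same population sentence also ends the maternal paragraph of 8.3, beside a near-duplicate, so its appearance under cord blood may be an editing remnant. Protocol section 7 calls its text a summary and leaves detail to the SAP. This is a fair reading of probable intent. It remains an inference, and the sentence in 8.3 and the protocol rule are still in force.
- **A conditional sensitivity analysis is legitimate.** Agreed: unconditional reporting is one repair, and a corrected denominator is another. The existing condition is neither.
- **The Visit 4 window is peripheral.** Also fair. It mainly concerns maternal responses, and would not affect cord blood if mITT is chosen. It is kept only as a minor note.
- **The stakes are small.** This is an exploratory objective on partly optional samples, with no alpha adjustment and no demonstrated effect on a result. That limits the importance of the point, but the rule is still wrong as written.

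**Conclusion.** Both parts hold. The share that would trigger the analysis is 0% by definition, against a required share above 10%, and this rests on no assumption. The primary population for cord blood is contradictory: SAP 6.3 and 9 point to mITT, while SAP 8.3 and Protocol 7.3.1 point to the Immunogenicity Population. The choice affects women without an in-window Visit 4 draw as well as violators, in numbers that the documents do not allow to be calculated. The counts of 44 and 41 assume an mITT denominator and only give scale; the upper figure of 4 window days assumes an elapsed-day reading.

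The consequence is confined to exploratory immunogenicity. The primary endpoint, power and secondary outcomes are unaffected. The text should nevertheless be corrected, because a prespecified analysis cannot run and the primary cord-blood result is not uniquely defined.

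**What to change.** Before the cord-blood analysis:

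1. Name one primary population for cord blood, identifying the objective by name and not by number, and make SAP 6.3, 8.3 and 9 and Protocol 7.3.1 agree.
2. State whether membership for cord blood requires the Visit 4 draw.
3. Drop the trigger and always report cord-blood results both in mITT women with evaluable cord samples and in the violation-excluded set. Alternatively, keep a trigger but define its denominator before exclusions, and say whether a missing draw (Appendix 1, item 2b) counts as a violation.
4. As a minor correction, reconcile the Visit 4 windows in Protocol 3.2.1, both places in Protocol 5.1, and SAP 4.2 into one stated range for population membership.

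The cost is wording in SAP 6.3, 8.3 and 9, plus Protocol 7.3.1 if mITT is chosen, and one consistent line wherever the Visit 4 window appears. No new data are needed. Always reporting both sets adds one further set of cord-blood results.
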